3.1 Study design

This study uses а 2-treatment arm, randomized, parallel-group, double-blind, placebo-controlled design in patients with PsA and axSpA. The dosing of secukinumab will be applied according to the approved European Summary of Product Characteristics (SmPC) in PsA and AS disease. In case of axSpA patients with objective signs of inflammation at screening, evident by either MRI with Sacroiliac joint inflammation (according to source documentation) and/or hsCRP > upper limit of normal (ULN, as defined by central lab), secukinumab/placebo will be applied as 1 (1.0 mL pre-filled syringe (PFS) of 150 mg dose) s.c. injection. At Baseline approximately 200 patients will be randomized. Randomization will occur to 1 of the following 2 treatment groups in a ratio of 1:1:

- Group 1 (secukinumab): secukinumab as 1 (1.0 mL pre-filled syringe (PFS) of 150 mg dose) s.c. or 2 (2 x 1.0 mL PFS of 150 mg dose, 300 mg) s.c. injections according to axSpA or PsA disease (including extent of psoriasis and TNF-inhibitor status) at Baseline, Weeks 1, 2, and 3, followed by administration every 4 weeks starting at Week 4.
- Group 2 (placebo): placebo as 1 (1.0 mL PFS) or 2 (2 x 1.0 mL PFS) s.c. injections according to axSpA or PsA disease (including extent of psoriasis and TNF-inhibitor status) at Baseline, Weeks 1, 2, 3, followed by administration every 4 weeks starting at Week 4.

Additionally, it is planned to enroll no more than 40% TNF-IR patients in the study.

Starting at Week 24, patients who have been randomized to placebo at Baseline will all switch to secukinumab. They will receive the dose according to their disease (PsA or axSpA). Therefore they will receive secukinumab 150 mg (1.0 mL PFS of 150 mg dose s.c.) or 300 mg (2 x 1.0 mL PFS of 150 mg dose s.c.). Secukinumab will be administered without a loading phase every 4 weeks (Figure 3-1). Thus, starting at Week 24, patients in both groups will receive secukinumab either 150 mg or 300 mg as 1 or 2 injections of 1 mL/150 mg in PFS in an open-label fashion until Week 52 (last dose given at Week 48). However, original randomized treatment assignment to secukinumab or placebo will remain double-blinded to all patients, investigators, and site personnel, whereas the Sponsor (including the Region Europe Clinical Team, statisticians and data management) will be unblinded after the Week 24 database lock (see Section 3.5) and analyses are completed (see Section 9.7).

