3.2 Rationale for study design

The double-blind, randomized, parallel-group, placebo-controlled design used in this study up to Week 24 is in alignment with phase III trials of other biologics in this disease area and in compliance with the European Medicines (Evaluation) Agency (EMA/EMEA) guidelines

Novartis	Confidential	Page 26
Amended Clinical Trial Protocol Version 03	clean	Protocol No. CAIN457F3301

(EMA 2005). Placebo group will be re-assigned to active treatment at Week 24. Unblinding of the Novartis Clinical Team will occur after the Week 24 database lock for primary endpoint analysis. Nevertheless all investigators, site personnel, patients, and monitors will continue to remain blinded to the original randomization to active treatment vs. placebo until the Week 52 database lock and analyses are completed so as to ensure reliable efficacy and safety assessments over time. All patients will be on secukinumab treatment from Week 24 up to Week 48. However, data up to 52 weeks is being generated to evaluate the safety and the sustainability of response in this population.

The patient population will be described in more detail in the Section 4 below.

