5.1 Study treatment

5.1.1 Investigational and control drugs

Novartis will supply the following:

• Study treatment:

Secukinumab 150 mg provided in 1 ml PFS.

• Placebo:

Secukinumab placebo provided in a 1 ml PFS.

The PFSs are packed in a double blinded fashion and do not need to be prepared. The study treatments will be labeled as follows:

- Double-blind secukinumab and placebo PFS will be labeled as AIN457 150 mg/1ml/Placebo for dosing till Week 24.
- Open-label secukinumab PFS will be labeled as AIN457 150 mg/1ml.

Note: The secukinumab PFSs are packed in double-blinded fashion until Week 24 when open-label treatment is started and, therefore, do not need to be prepared by the study site. Starting at Week 24, open-label medication will be supplied until the last dose is given at Week 48.

For detailed instructions on the storage of the study treatments, please refer to Section 5.5.3.

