**Figure 1: Study design****Planned number of patients and randomization**

At Baseline approximately 200 patients will be randomized. Randomization will occur to one of the following two treatment groups in a ratio of 1:1.

- Group 1 (secukinumab): secukinumab as 1 (1.0 mL pre-filled syringe (PFS) of 150 mg dose) s.c. or 2 (2 x 1.0 mL PFS of 150 mg dose, 300 mg) s.c. injections according to axSpA or PsA disease at Baseline, Weeks 1, 2, and 3, followed by administration every 4 weeks starting at Week 4.
- Group 2 (placebo): placebo as 1 (1.0 mL PFS) or 2 (2 x 1.0 mL PFS) s.c. injections according to axSpA or PsA disease at Baseline, Weeks 1, 2, 3, followed by administration every 4 weeks starting at Week 4.

Patients will receive study treatment at Baseline, Weeks 1, 2, and 3, followed by treatment every 4 weeks through Week 52 (last dose given at Week 48). At Week 24, patients originally randomized to placebo will switch to receive secukinumab 150 mg (1 injection of secukinumab 1 mL/150 mg) or secukinumab 300 mg (2 injections of secukinumab 1 mL/150 mg) in open-label fashion without a loading regimen.

Blinding to the original treatment assignment will be maintained until after the Week 52 database lock and analyses are completed. However, original randomized treatment assignment to secukinumab or placebo will remain double-blinded to all patients, investigators, and site personnel, whereas the Sponsor (including the Region Europe Clinical Team, statisticians and data management) will be unblinded after the Week 24 database lock (protocol [Section 3.5](#)) and analyses are completed (protocol [Section 9.7](#)).

Patients will be stratified at randomization on the basis of PsA or axSpA disease.

Based on enrollment target, it is planned that approximately 50% of randomized patients should be PsA and approximately 50% axSpA patients to ensure a balanced patient population for the assessment of efficacy and safety.

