## 2.2 Analysis sets

The following analysis sets will be used in this trial:

**Randomized set:** The randomized set will be defined as all patients who were randomized. Unless otherwise specified, miss-randomized patients (miss-randomized in IRT) will be excluded from the randomized set.

Mis-randomized subjects are defined as those subjects who were mistakenly randomized into the IVR prior to the site confirming all eligibility criteria had been met and to whom no study medication was given.

**Full analysis set (FAS):** The FAS will be comprised of all patients from the randomized set to whom study treatment has been assigned. Following the intent-to-treat principle, patients will be evaluated according to the treatment assigned to at randomization. For patients randomized erroneously into the wrong stratum, the actual stratum will be used for analyses.

**Safety set:** The safety set includes all patients who took at least one dose of study treatment during the treatment period. Patients will be evaluated according to treatment received.

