### **Switching from placebo to secukinumab at Week 24**

At Week 24, patients originally randomized to placebo will switch to receive secukinumab 150 mg (1 injection of secukinumab 1 mL/150 mg) or secukinumab 300 mg (2 injections of secukinumab 1 mL/150 mg) in open-label fashion without a loading regimen.

Summary statistics will be provided for:

- Number and percentage of patients with resolution of Achilles tendon enthesitis after switching from placebo to secukinumab at Week 24.
- Mean change of heel pain in patients after switching from placebo to secukinumab at Week 24.

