### **2.8 Safety analyses**

For all safety analyses, the Safety set will be used.

Summaries will be performed separately for first (Week 1-24) and entire treatment periods. Use of data up to and including the last visit before rescue provides and unbiased comparison between secukinumab and placebo; data collected beyond week 24 are included in analyses which summarize the entire treatment period.

Safety analyses will be performed by PsA and AxSpA patients on treatment received or actual treatment as described below:

The actual treatment or treatment received for summaries of safety data will differ to the treatment assigned at randomization only if a subject received the wrong treatment during the entire study.

For those patients who received not the treatment randomized, i.e. who received erroneously the wrong treatment at least once, an additional AE listing will be prepared displaying which events occurred after the treatment errors.

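### SAP 2.8 defines actual treatment for safety only over the whole study, so, read literally, a full drug swap before Week 24 stays uncorrected in the Week 1-24 tables for patients who continue

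*SAP*

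**What the plan says.** The Safety set definition in SAP 2.2 reads "Patients will be evaluated according to treatment received". Protocol 9.1 has the same definition, and neither document adds a condition on duration there.

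SAP 2.8 then says how treatment received is to be determined. It differs from the randomised treatment "only if a subject received the wrong treatment during the entire study". For anyone given the wrong treatment at least once, the section adds a listing of the events that followed the error.

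On reporting periods, SAP 2.8 states: "Summaries will be performed separately for first (Week 1-24) and entire treatment periods".

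On treatment after Week 24, Protocol 3.1 says that "starting at Week 24, patients in both groups will receive secukinumab either 150 mg or 300 mg", and Protocol 3.2 says "All patients will be on secukinumab treatment from Week 24 up to Week 48". Protocol 5.1.1 describes the supply: "Starting at Week 24, open-label medication will be supplied until the last dose is given at Week 48". SAP 2.7.2 agrees for the control arm: "patients originally randomized to placebo will switch to receive secukinumab 150 mg".

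SAP 2.1.1 defines study treatment as the product, that is, the secukinumab syringe or the placebo syringe.

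**The concern.** The rule looks at the whole study, while the tables that matter most for comparative safety cover only Week 1-24. Because both arms receive secukinumab from Week 24, a secukinumab/placebo swap ends there by design for every patient who continues as planned. A rule that requires the error to last throughout then cannot be met, however complete the error was while the arms differed.

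Two things follow on the literal reading. Events on secukinumab can be tabulated under placebo, or the reverse, in the only period with a placebo comparison. And two patients with the same exposure before Week 24 can fall in different columns because one stayed in the study and the other left.

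The point concerns patients who were given the wrong drug. The planned move of placebo patients to secukinumab at Week 24 is not an error and is not in question.

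**Working it through.** There is no stated figure to reproduce. The check applies the rule to the dosing schedule.

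**Inputs**
- Dosing visits before Week 24 (Protocol Table 6-1): Baseline and Weeks 1, 2, 3, 4, 8, 12, 16 and 20, which is 9.
- Dosing visits from Week 24: Weeks 24, 28, 32, 36, 40, 44 and 48, which is 7. The total is 9 + 7 = 16.
- Planned drug: Group 1 has secukinumab at all 16 visits; Group 2 has placebo at 9, then secukinumab at 7.
- Rule (SAP 2.8): reassign only if the treatment was wrong throughout. The patient's own time in the study is taken as the entire study.

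**Rule applied to three records**

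| Randomised to | Given before Week 24 | From Week 24 | Wrong visits | Column under the literal rule | Drug received in Week 1-24 |
|---|---|---|---|---|---|
| Secukinumab | Placebo at all 9 | Secukinumab at 7 | 9 of 16 (56%) | Secukinumab | Placebo |
| Placebo | Secukinumab at all 9 | Secukinumab at 7 | 9 of 16 (56%) | Placebo | Secukinumab |
| Placebo | Secukinumab only, stops before Week 24 | None | All | Secukinumab (reassigned) | Secukinumab |

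Counted within Week 1-24 only, before the Week 24 dose, the first two patients are wrong at 9 of 9 visits, and a per-period rule would move them.

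**Size**

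The documents give no expected number of such patients and no adverse event rates for this trial, so both are assumed here. Take 100 patients per column, true rates pS on secukinumab and pP on placebo, and k patients randomised to placebo who received secukinumab but stay in the placebo column.

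- Placebo column rate = [(100 − k) × pP + k × pS] / 100
- Displayed difference = pS − placebo column rate = (1 − k/100) × (pS − pP)

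| pS vs pP | True difference | k = 1 | k = 5 |
|---|---|---|---|
| 10% vs 5% | 5.0 points | 5.05% on placebo; 4.95 points | 5.25% on placebo; 4.75 points |
| 60% vs 50% | 10.0 points | 50.1% on placebo; 9.9 points | 50.5% on placebo; 9.5 points |

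For a single rare event, one such patient turns 0 of 100 into 1 of 100 on placebo.

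**The case against.** The strongest reply is that the failure depends on how treatment is read. SAP 2.8 compares treatment received with what was assigned at randomisation, and what is assigned is an arm with a 52-week regimen. Protocol 5.2 describes Group 2 as placebo followed by secukinumab, and the on-treatment definition in SAP 2.1.1 splits that group into 24 weeks of placebo and 28 of secukinumab. On that reading the second record received Group 1's whole sequence, the first received Group 2's, and both are reassigned. This is a possible reading. But the SAP does not state it, and its own definition of study treatment names the product. The text needs to settle the question.

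A reader might infer that SAP 2.8 contradicts the Safety set definition. The documents do not support that. SAP 2.2 leaves treatment received undefined for mixed exposure, and SAP 2.8 offers its rule as the working definition. Some such rule is needed. The trouble is that this one does not fit the Week 1-24 tables.

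A reader might also infer that the exception can never apply to anyone treated past Week 24. That goes too far: a wrong dose level (150 mg against 300 mg) could persist to Week 48. The point is limited to secukinumab/placebo swaps.

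It is fair to add that the event is remote. Kits are assigned by medication number through the IRT (Protocol 5.3, 5.5.2), and doses up to Week 24 are given at the site (Protocol 5.5.4). Cases would also be visible through the adverse event listing, the tabulation of protocol deviations, which include dosing errors in the comparative phase (SAP 2.3.1, 5.5), and the counts of active and placebo injections by group (SAP 2.4.1). All of this stands and keeps the point small. None of it moves a patient between columns.

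**Conclusion.** The point holds as a minor one. SAP 2.8 has no rule for actual treatment that matches its own Week 1-24 reporting period. On the literal, product-based reading it leaves a complete swap uncorrected in patients who continue, while correcting the same swap in patients who stop early.

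Each affected patient is about 1 in 100 of a column, so a crude rate moves by at most about 1 percentage point per patient. With an assumed 1 to 5 such patients, a true difference shrinks by 1% to 5% of its size. That matters little for common events. A single serious event could still be shown under the wrong drug.

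Nothing in the documents suggests that such patients are expected. A reader might infer that the trial's safety comparison as a whole, or its efficacy result, is unreliable for this reason. Neither follows: the effect per patient is small, and efficacy is analysed as randomised in the FAS (SAP 2.2). The conclusion rests on reading treatment as the product and on the patient otherwise following the planned schedule after Week 24.

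**What to change.** Replace the sentence in SAP 2.8 with:

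> For Week 1-24 safety summaries, actual treatment is the randomised treatment unless every dose taken before the Week 24 dose was the other arm's drug, in which case it is the drug received. For entire-treatment-period summaries, the patient is assigned to the treatment sequence actually received (secukinumab throughout, or placebo then secukinumab) under the same condition.

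The cut-off should be the Week 24 dose, not the end of Treatment Period 1. Table 6-1 places the Week 24 visit, with its open-label dose, under that period. Counting it would make the swapped patient wrong at 9 of 10 doses and bring the problem back. The wording also covers patients who stop early.

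Keep the additional adverse event listing for patients with isolated dosing errors. They stay in the randomised column, as they do now.

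The cost is a two-sentence replacement in the SAP and an actual-treatment variable derived for each reporting period. No trial procedure changes.

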### **2.8.1 Adverse events (AEs)**

The crude incidence of treatment emergent adverse events (i.e. events started after the first dose of study treatment or events present prior to the first dose of study treatment but increased in severity based on preferred term) will be summarized by primary system organ class and preferred term. Confidence intervals for the crude rate will be derived as described in Section

In addition, exposure time-adjusted rates (incidence rate) including 95% confidence intervals will be provided for the entire treatment period to adjust for differences in exposure between treatment groups. Graphical displays of the crude incidence and exposure-adjusted rates will be presented for all AEs and serious AEs by system organ class.

Treatment emergent adverse events reported will be presented by preferred term in descending frequency according to its incidence in total secukinumab group (combining all secukinumab treatment groups) starting from the most common event. Summaries (crude incidences only) will also be presented for AEs by severity and for study treatment related AEs. If a particular AE 'severity' is missing, this variable will be listed as missing and treated as missing in summaries. If a subject reported more than one adverse event with the same preferred term, the adverse event with the greatest severity will be presented. If a subject reported more than one adverse event within the same primary system organ class, the subject will be counted only once with the worst severity at the system organ class level, where applicable.

Separate summaries will be provided for

- adverse events suspected to be related to study drug by the investigator
- deaths
- serious adverse events
- adverse events leading to discontinuation
- adverse events leading to temporary dose interruption

Adverse events will also be reported separately by MedDRA SMQ.

For all adverse event summaries, the MedDRA version used for reporting the study will be described in a footnote.

Adverse event summaries will also be provided for the follow-up period for all patients (completers and early discontinuations).

A listing of non-treatment emergent adverse events will be provided. These cover adverse events that occurred before the first dose of the study treatment. The crude incidence will be provided without treatment information.

Algorithms for date imputations will be provided in Programming Specifications.

For SAEs that occurred during screening a listing will be prepared for all patients screened including screening failures.

**Table 2.8-1 Overview of analyses on some safety endpoints**

Analysis period	AEs & SAEs	AEs by severity	Study drug related AEs	AEs-SMQ	Risk	Notables for (vitals/ECG), lab criteria
Day 1 – Week 24	• crude incidence	• crude incidence	• crude incidence	• crude incidence	• crude incidence	• crude incidence
Day 1 – Week 24	• exposure time adjusted incidence*					
Entire Treatment (up to week 52)	• crude incidence • exposure time adjusted incidence*	• crude incidence	• crude incidence	• exposure timeadjusted incidence	• crude incidence exposure time adjusted incidence	• crude incidence

\*Exposure-adjusted incidence rates will be done for the following:

- at the PSOC for AE and SAE
- at the PT level for common AEs, which is defined as at least 2% of the patients in the combined AIN457 groups during the initial treatment period or events that had an incidence rate of at least 5.0 cases per 100 subject-years in the combined AIN457 groups during the entire treatment period
- at Level 1 for Risks and SMQ analyses

### 2.8.1.1 Adverse events of special interest / grouping of AEs

Safety topics of interest, such as risks defined in the Safety Profiling Plan (SPP), Risk Management Plan or topics of interest regarding signal detection or routine analysis are defined in the Program Case Retrieval Sheet that is stored in CREDI at the path Cabinets/CREDI Projects/A/AIN457A/Integrated Medical Safety.

The crude incidence and exposure-adjusted incidence rates for SPP risks will be summarized. In addition, listings will be provided presenting which subjects experienced which risk.

Important note: For the evaluation of SPP risks primary and secondary system organ classes of the MedDRA dictionary will be considered.

### 2.8.2 Deaths

Separate summaries and listings will be provided for deaths for each treatment period.

### 2.8.3 Laboratory data

The summary of laboratory evaluations will be presented by patient sub-population for three groups of laboratory tests (hematology, serum chemistry and urinalysis). Descriptive summary statistics for the change from Baseline to each study visit will be presented in tabular and graphical fashion.

These descriptive summaries will be presented by test group, laboratory test and treatment group. Change from Baseline will only be summarized for patients with both Baseline and Post-Baseline assessments.

For each parameter, the maximum change from Baseline within each study period will be analyzed analogously.

QuantiFERON TB-Gold test will also be analyzed by the central laboratory.

In addition, shift tables will be provided for all parameters to compare a subject's baseline laboratory evaluation relative to the visit's observed value. For the shift tables, the normal laboratory ranges will be used to evaluate whether a particular laboratory test value was normal, low, or high for each visit value relative to whether or not the baseline value was normal, low, or high. If appropriate, the shifts to the most extreme laboratory test value within a treatment phase (either initial or entire) will be presented as well (including category "high and low"). These summaries will be presented by laboratory test and treatment group.

The following laboratory parameters will be analyzed with respect to numerical Common Terminology Criteria for Adverse Events (CTCAE) grades, given in Table 2.8-2: Hematology will include hemoglobin, platelets, red blood cells (RBC), white blood cells (WBC), differential WBC counts. Serum chemistry will include glucose, cholesterol, triglycerides (TG), urea, creatinine, total bilirubin (TBL), AST (SGOT), ALT (SGPT), gamma-glutamyl transferase (GGT), alkaline phosphatase (ALP), sodium, potassium, bicarbonate, calcium, phosphorous, total protein, albumin, and uric acid. The urinalysis results for standard parameters such as protein, glucose, blood and WBCs will be recorded in the appropriate eCRF page.

These summaries will be split into hematology and chemistry for study level reports and the pooled summary of clinical safety.

